### Answer/Response:

Building on pilot work from our team exploring green space activity type, this study aims to focus specifically on older adults in Charlottesville and the surrounding areas. We aim to understand how green space activity type may influence belonging, loneliness and mood and how this may impact on willingness to return to JABA centers. Our research questions are as follows;

1. What types of green space activities have a beneficial impact on loneliness, belonging and mood in seniors who are JABA center members?
2. Does the inclusion of these activities encourage JABA service users to continue participation at their JABA centers?

To investigate these questions, we will utilize 2 study components. The first, titled 'activity sessions' refers to a participant group who will undergo a series of activities (on separate days) including walking, citizen science and planting in order to understand pre- and post-activity wellbeing. The second component, titled 'survey-only', refers to a different participant group who are remotely surveyed on their current wellbeing, experiences during COVID and barriers on returning to JABA. All participants will be JABA service users.

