## Study Design: Biomedical

### 1. Will controls be used?

Answer/Response: Yes

► IF YES, explain the kind of controls to be used.

Answer/Response: There are two controls. First, during the activity sessions, participants will act as their own control, crossing over to take part in each activity. Second, we also will conduct a survey remotely in which participants will respond to questions regarding their current wellbeing. These will be compared to those of the participants who undergo the activity sessions.

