### 2. What is the study design?

Example: case series, case control study, cohort study, randomized control study, single-blind, double-blind, met-analysis, systematic reviews, other. You may also view the IRB-HSR Learning Shot on this topic to help you answer this question.

[https://hrpp.irb.virginia.edu/learningshots/Writing\\_protocol\\_June09/player.html](https://hrpp.irb.virginia.edu/learningshots/Writing_protocol_June09/player.html)

Answer/Response: For the activity sessions, the study is a repeated measures study design. For the survey only group, the study is a single cohort study.

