**2. Describe expected rate of screen failure/ dropouts/withdrawals from all sites.**

**Answer/Response:**

We would expect around 10% attrition, so a final sample of 54 (n = 27 per group) is expected

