**4. What is your plan for primary variable analysis?**

UVA Study Tracking: HSR210100

Version Date: 03-22-21

Page Number: 6 of 11

Include primary outcome(s)/predictor variable(s), statistical methods/models/tests to be employed, or descriptive summaries as appropriate. If not applicable, please provide explanation.

**Answer/Response:** We will use the following outcome measures across the study.

- Loneliness; measured by the UCLA Loneliness Scale, a 3-item scale that captures feelings of loneliness. (Activities and survey-only)
- Belonging; measured by the General Belonging Scale (GBS), a 12-item scale capturing social acceptance/inclusion and social rejection/exclusion. (Activities and survey-only)
- Acute Mood; pre and post measures of mood will be taken using the UWIST Mood Adjective Checklist (MACL), an acute measure of hedonic tone, stress and arousal. (Activities only)
- Restoration; Psychological restorative qualities of the setting measured by the Perceived Restorativeness Scale, a three point scale determining the restorative quality of activity spaces. (Activities only)
- Physical Activity; In addition to the arousal measure of the MACL, we will use the 10 point scale of the OMNI Perceived Exertion scale, to understand how physically exerted participants feel between activities. To understand baseline physical activity, we use the international physical activity questionnaire (IPAQ) to compare between studies (Activities and survey-only).
- Accelerometer; we will use accelerometers to measure participant movement throughout the activities to correlate with physical activity measures. (Activities only). Specifically, we will look to understand if increased movement, as measured by the accelerometer, correlates with increased feelings of exertion post-activity (across all three activities).

For measures taken in both the activities and survey-only, we will use an independent t-test using condition (activity or survey) to compare. For activities that use pre- and post-assessments, we will make change scores for each and use this in a one-way ANOVA, using activity type (three levels; walking, citizen science, planting) as the grouping variable.

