**Answer/Response:**

There are two components to this study, so we describe each separately. *Activity sessions*

There will be three activity sessions, the protocol for each is largely the same. For the walking and the citizen science sessions, participants will be transported (Jaunt bus) to a nature preserve to conduct this session. Alternatively, if participants wish to transport themselves, they are welcome to – this will be confirmed after obtaining consent. The planting session is held at the JABA center. Upon arrival at the given site, participants will be given their initial pre-activity survey to complete (pen and paper) and are given an accelerometer to wear throughout the study session. Following this, they will undertake their activity; this will include a short nature walk, a guided citizen science walk or a session planting and tending to greenery in raised beds. At the end of the sessions (up to 30 minutes), participants will complete the post-activity survey and remove their accelerometer. After payment (\$10 supermarket voucher per session), participation ends.

*Survey Only*

Participants are mailed a study information sheet and the the survey with a return envelope. They are asked to complete the survey and return it to the research team.

**1. If this protocol involves study treatment, explain how a subject will be transitioned from study treatment when they have completed their participation in the study.**

**Example:** If the subject will be taking an investigational drug, will they need to be put back on an approved drug when they have completed the study? If yes, explain how this will be accomplished and who will cover the cost. If the subject has a device implanted will it be removed? Again- who will cover the cost of the removal?

**Instructions:** Answer NA if this study does not involve a study treatment.

**Answer/Response:** N/A

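### The same participants do all three activities, but their change scores are to be compared with a one-way ANOVA that has no participant term

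*Combined protocol and SAP*

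**What the plan says.** The design sections agree with one another. Objectives/Hypothesis describes "a participant group who will undergo a series of activities (on separate days) including walking, citizen science and planting". Study Design: Biomedical, question 1, says that "participants will act as their own control, crossing over to take part in each activity", and question 2 says: "For the activity sessions, the study is a repeated measures study design". In Study Procedures, question 1, "There will be three activity sessions, the protocol for each is largely the same", and each session has a survey before and after the activity. A participant who attends all three sessions therefore contributes three change scores.

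The analysis is under Statistical Considerations, question 4. Outcomes with pre and post assessments become change scores, and the plan is to "use this in a one-way ANOVA, using activity type (three levels; walking, citizen science, planting) as the grouping variable". Mood (the UWIST checklist) is the only outcome described there as measured before and after. Measures collected in both components, such as loneliness and belonging, go to a different test: "For measures taken in both the activities and survey-only, we will use an independent t-test using condition (activity or survey) to compare".

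No section mentions a participant factor, a repeated-measures ANOVA or a mixed model. The secondary analysis (question 5) is not applicable, and question 6 says no statistician was involved.

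**The concern.** A one-way ANOVA with activity as the grouping variable compares separate groups of people. Here the three groups are the same people. Taking change scores keeps the link between pre and post within a session, but the link across a person's three sessions is lost, and with it the own-control feature that the design claims.

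The direction of the error depends on the correlation, rho, between a person's change scores. If rho is positive, the error term includes between-person variation that the design could remove, so real differences between activities are missed. If rho is negative, the error term is too small and false positives rise. This is the only test named for comparing activities, so the mood part of research question 1 depends on it. It does not reach loneliness, belonging or research question 2.

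**Working it through.** **Inputs from the documents.** Sixty are enrolled and about 10% attrition is expected (Human Participants, Subjects, questions 2 and 3). The plan's own figure reproduces: 60 × (1 − 0.10) = 54, and 54 / 2 = 27, matching "a final sample of 54 (n = 27 per group) is expected". There are three activities.

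**Assumptions, none in the documents.** Alpha 0.05; change-score SD 1; equal correlation rho between a person's three scores; normal data; all 27 complete all three sessions; no order or period effect; for power, one activity better than the other two by 0.5 SD.

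**Degrees of freedom.** Scores: 27 × 3 = 81. One-way ANOVA error df: 3 × (27 − 1) = 78. Repeated-measures error df: (3 − 1) × (27 − 1) = 52.

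**Why the stated test misbehaves.** With variance 1 and no activity effect, the expected mean squares are:

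- activity: 1 − rho
- one-way error: 1
- repeated-measures error: 1 − rho

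The repeated-measures ratio compares like with like. The one-way ratio is centred near 1 − rho: 0.7 at rho 0.3 (conservative) and 1.2 at rho −0.2 (too many false positives).

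**Type I error** (simulation, 200,000 trials per cell):

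| rho | Stated one-way F (2, 78) |
|---|---|
| −0.2 | 8.1% |
| −0.1 | 6.5% |
| 0 | 5.0% |
| 0.1 | 3.6% |
| 0.3 | 1.5% |
| 0.5 | 0.4% |

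Over the same range the repeated-measures F (2, 52) stays at 4.9 to 5.0%, the same test with Greenhouse-Geisser correction at 4.5 to 4.7%, and the unstructured-covariance test at 4.9 to 5.1%.

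**Power for the 0.5 SD difference:**

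| rho | Stated | Repeated measures | With correction | Unstructured |
|---|---|---|---|---|
| 0 | 44.8% | 44.0% | 42.6% | 41.6% |
| 0.1 | 43.5% | 48.1% | 46.6% | 45.6% |
| 0.3 | 40.3% | 58.7% | 57.3% | 56.0% |
| 0.5 | 36.9% | 74.4% | 73.2% | 71.4% |

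**Analytic check.** The activity means 0, 0 and 0.5 have squared deviations from their average summing to 1/36 + 1/36 + 4/36 = 1/6. The noncentrality for the repeated-measures test is 27 × (1/6) / (1 − rho) = 4.5 / (1 − rho), which is 4.50, 6.43 and 9.00 at rho 0, 0.3 and 0.5. The noncentral F distribution then gives power of 43.8, 58.9 and 74.5% for repeated measures and 41.5, 56.1 and 71.6% for the unstructured test, in agreement with the simulation.

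**The case against.** The strongest reply is that this is loose wording. One-way counts factors, and a one-way repeated-measures ANOVA is still one-way; read beside the declared repeated measures design, the sentence could mean the within-person test. That reading is possible, but calling activity a grouping variable is between-groups language, and an analyst who follows the text would run the wrong test. The sentence needs changing on either reading.

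Second, this is a pilot with a sample size set by feasible recruitment and no stated alpha, power or decision rule, and under positive correlation the error is conservative. That limits the consequences but does not make the test match the design. The plan does commit to a hypothesis test, and with so few participants lost power matters.

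Third, the harm rests on an assumed rho. This stands. Differencing removes stable differences in mood level between people, so a small rho cannot be excluded, and the documents give no reason to expect a negative one. The figures show a range, not an estimate.

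Two conditions also stand. The 27 per group is an expected final sample, not a count of people who attend all three sessions, and missed sessions were not simulated. No randomization is planned and no activity order is given, so a participant term would not separate activity from order; that is a separate issue.

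**Conclusion.** The concern holds: the analysis as written does not match the declared design and should be corrected before the data are analysed. The mismatch itself rests only on the protocol's text. Its size rests on the assumptions listed above. For rho from −0.2 to 0.5, the type I error of the stated test runs from 8.1% down to 0.4%. Compared with the uncorrected repeated-measures F, it loses 58.7 − 40.3 = 18.4 points of power at rho 0.3 and 74.4 − 36.9 = 37.5 points at rho 0.5. Near rho 0 the choice makes little difference. The reach is the comparison of activities on mood.

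**What to change.** In Statistical Considerations, question 4, replace the one-way ANOVA with a repeated-measures ANOVA on the change scores: activity as a three-level within-person factor, participant as the repeated unit, and a sphericity correction such as Greenhouse-Geisser. To keep participants who miss a session, specify instead a mixed model for repeated measures with unstructured within-person covariance (or compound symmetry that allows negative covariance) and small-sample degrees of freedom. A random-intercept model with its variance bounded at zero is not a safe substitute if rho may be negative: its type I error was 8.1% at rho −0.2 and 6.7% at −0.1.

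The cost is one sentence, with no extra participants, visits or measurements. The pen-and-paper surveys must be linkable by participant across the three sessions, which the plan should confirm. At rho 0, power falls from 44.8% to 44.0% (repeated-measures F), 42.6% (with correction) or 41.6% (unstructured), so by about 1, 2 or 3 points. At rho −0.2 the stated test appears more powerful (46.9% against 37.4% for the repeated-measures F), but only because its type I error is 8.1%.

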##### **5. What is your plan for secondary variable analysis?**

Include the following:

- Secondary outcome(s)/predictor variables, statistical methods/models/tests to be employed, or descriptive summaries as appropriate. If not applicable, please provide explanation.
- For phase III studies, the power/precision of the study to address the secondary objective(s).

**Answer/Response:** N/A

##### **6. Have you been working with a statistician in designing this protocol?**

Consultation with a professional statistician is highly recommended to ensure good science of the study and facilitate the review process.

**Answer/Response:** No

**IF YES, what is their name?**

Answer/Response:

**7. Will data from multiple sites be combined during analysis?**

Answer/Response: No

INSTRUCTIONS: IF YES, answer the following questions

**7(a). Does the study involve randomization?**

Answer/Response:

**IF YES, will randomization be done at each site or among sites?**

Answer/Response:

**7(b). Has the sample size calculation considered the variation among sites?**

Answer/Response:

**7(c). When combining the data from multiple sites to assess the study results, is the effect of the treatment to be tested (or the association to be tested) assumed to be the same across sites or vary among sites? What is the modelling strategy?**

Answer/Response:

**7(d). Is there a common protocol used in all sites?**

Answer/Response:

**IF NO, how will differences among sites, such as those related to the implementation, inclusion criteria, patient characteristics, or other sites characteristics, be considered to assess the study results?**

Answer/Response:

## Study Procedures-Biomedical Research

**1. What will be done in this protocol?**

**INSTRUCTIONS:**

This should include everything that will be done as part of this protocol. Do not repeat information that is included in other sections such as Background or Hypothesis sections.

This section should include an indication of which research interventions if any offer a prospect for direct benefit and which interventions (invasive measurements, collection of blood, tissue, data, surveys, etc.) are being done solely to answer a research question and generate generalizable knowledge. If the interventions done solely for research purposes are associated with greater than minimal risk they need to be justified. Describe and justify any control and experimental arm and include method, dose, and duration of drug administration. Reference any claim of clinical equipoise if applicable.

If you are obtaining specimens or data, provide information regarding the type of specimen/data, amount of specimen needed and how the specimen/data will be obtained and what analysis will be done with the specimen/data.

**Special note for studies with waiver of consent/waiver of documentation of consent:**  
Include a statement regarding how subjects will be recruited. For other studies this information is captured in Recruitment does not need to be duplicated in this section.

**Answer/Response:**

There are two components to this study, so we describe each separately. *Activity sessions*

There will be three activity sessions, the protocol for each is largely the same. For the walking and the citizen science sessions, participants will be transported (Jaunt bus) to a nature preserve to conduct this session. Alternatively, if participants wish to transport themselves, they are welcome to – this will be confirmed after obtaining consent. The planting session is held at the JABA center. Upon arrival at the given site, participants will be given their initial pre-activity survey to complete (pen and paper) and are given an accelerometer to wear throughout the study session. Following this, they will undertake their activity; this will include a short nature walk, a guided citizen science walk or a session planting and tending to greenery in raised beds. At the end of the sessions (up to 30 minutes), participants will complete the post-activity survey and remove their accelerometer. After payment (\$10 supermarket voucher per session), participation ends.

*Survey Only*

Participants are mailed a study information sheet and the the survey with a return envelope. They are asked to complete the survey and return it to the research team.

**1. If this protocol involves study treatment, explain how a subject will be transitioned from study treatment when they have completed their participation in the study.**

**Example:** If the subject will be taking an investigational drug, will they need to be put back on an approved drug when they have completed the study? If yes, explain how this will be accomplished and who will cover the cost. If the subject has a device implanted will it be removed? Again- who will cover the cost of the removal?

**Instructions:** Answer NA if this study does not involve a study treatment.

**Answer/Response:** N/A

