**2. What are the statistical considerations for the protocol?**

The objectives section and the statistical section should correspond, and any objective for which analysis is unfeasible should be deleted. Also, the estimates and non-statistical assumptions of the statistical section should be supported by discussion in the background section.

The answer to this question should include:

- Study Design/Endpoints
- Recap of study objectives and endpoint definitions. An assessment of how study objectives will be assessed by identifying & defining which endpoints will be used to assess each component of the study objectives.
- The study design should include contingencies for early stopping, interim analyses, stratification factors (if applicable), and any characteristics to be incorporated in analyses.
- The power/precision of the study to address the major study endpoint(s), the assumptions involved in the determination of power/precision.
- If statistical hypothesis testing is included then specify the null and alternative hypotheses, the test statistic, and the type I and II error rates
- If precision of an estimate, then provide a definition for precision
- If other, then specify

Answer/Response:

This is a pilot study aimed at ascertaining impacts of outdoor activities on both wellbeing as well as understanding barriers to returning to JABA centers.

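### Planting is done at the center and the other two activities at a preserve, so the overall test and any planting difference measure activity plus place; the one-way ANOVA also ignores the repeated measures

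*Combined protocol and SAP*

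**What the plan says.** Study Procedures, question 1, fixes the place of each session. "For the walking and the citizen science sessions, participants will be transported (Jaunt bus) to a nature preserve to conduct this session"; participants may also travel there themselves. By contrast, "The planting session is held at the JABA center". The pre-activity survey is completed after arrival at the site and the post-activity survey at the end of a session of up to 30 minutes.

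Statistical Considerations, question 4, says the team will form change scores and "use this in a one-way ANOVA, using activity type (three levels; walking, citizen science, planting) as the grouping variable". There is no place term, and no pairwise comparison is named.

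Study Design, question 1, says that "participants will act as their own control, crossing over to take part in each activity", and question 2 that "For the activity sessions, the study is a repeated measures study design". Objectives/Hypothesis gives the influence of green space activity type as the aim. Background frames walking as the default activity, citizen science as the cerebral one and planting as the physical one.

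**The concern.** Nobody plants at the preserve, and nobody walks or does citizen science at the center. If the planting change score differs from the others, the cause may be the activity, the place (including the trip to it), or both. The plan would label the difference as activity type. What a pilot passes on is its reading of the results. The risk here is carrying forward a statement that physical activity does better or worse than the other kinds when the difference may be center against preserve.

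A second error sits in the same sentence of the plan. The same people give all three change scores, but a one-way ANOVA with activity as the grouping variable treats them as three separate groups. Its error rate is then wrong. The two errors are best corrected together: a correct within-person model is more sensitive to any difference between sessions, including one caused by place, so the label matters more once the model is right.

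**Working it through.** **Inputs from the documents.** Session places: Study Procedures, question 1. Analysis factor and outcome: Statistical Considerations, question 4. Sample: Human Participants, question 2, where "a final sample of 54 (n = 27 per group) is expected". This reproduces: 60 × (1 − 0.10) = 54, and 54 / 2 = 27 in the activity component. The plan gives no power calculation, SD or within-person correlation, so there is no other figure to reproduce.

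**Step 1: can activity and place be separated?** Write the mean change as activity effect plus place effect.

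- Walking: a_W + p_preserve
- Citizen science: a_C + p_preserve
- Planting: a_P + p_center

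The pairwise differences are:

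- Planting − walking = (a_P − a_W) + (p_center − p_preserve)
- Planting − citizen science = (a_P − a_C) + (p_center − p_preserve)
- Citizen science − walking = a_C − a_W

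With columns walk, citizen science, planting, preserve, the three rows are (1,0,0,1), (0,1,0,1) and (0,0,1,0). The fourth column is the sum of the first two, so the rank is 3 of 4. Two of the three differences, and hence the overall F test, contain the place term. More participants do not change this.

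**Step 2: does the on-site pre-survey remove the place effect?** In part. If a place shifts mood by k at both surveys, k cancels in post minus pre. If the shift is k at the first survey and k + g at the second, g stays in the change score. Effects that build up during the session, or travel effects that wear off during it, are of this second kind.

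**Step 3: does the crossover remove it?** No. It removes differences between people. Each person plants only at the center, so place differs within every person's own comparison.

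**Step 4: error rate of the planned ANOVA.** Assumptions not in the documents: normal change scores with SD 1, equal correlation ρ between a person's three scores, complete data on n = 27, alpha 0.05. With no true difference:

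- between-activity sum of squares ~ (1 − ρ) × chi-square(2)
- within-activity sum of squares ~ (1 + 2ρ) × chi-square(26) + (1 − ρ) × chi-square(52)
- critical value of F(2, 78) = 3.114

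Let c = 2 × 3.114 / 78 = 0.0798. Because half a chi-square(2) is exponential, the rejection probability is exactly

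[1 + c(1 + 2ρ)/(1 − ρ)]^(−13) × (1 + c)^(−26).

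The second factor is 1.0798^(−26) = 0.1357.

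| ρ | First factor | Rejection rate |
|---|---|---|
| 0 | 1.0798^(−13) = 0.368 | 0.050 |
| 0.3 | 1.1825^(−13) = 0.113 | 0.015 |
| 0.5 | 1.3194^(−13) = 0.0273 | 0.0037 |
| 0.7 | 1.6387^(−13) = 0.00163 | 0.0002 |

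The row for ρ = 0 returns the nominal 5%, which checks the formula. Simulation with 1,000,000 runs per ρ agrees: 0.0152, 0.0036 and 0.0002 for ρ = 0.3, 0.5 and 0.7.

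**The case against.** The strongest reply is that activity as delivered is a reasonable target. The first research question asks which activities have a beneficial impact, and the second asks whether offering them encourages continued participation at the centers. The study describes itself in modest terms: "This is a pilot study aimed at ascertaining impacts of outdoor activities on both wellbeing". This stands as far as it goes. Each activity's own pre-to-post change is usable as the change seen with that activity at its place. It does not rescue a comparison labelled activity type, which is the stated aim and the frame given in the Background.

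It may also be said that the plan measures setting: "Psychological restorative qualities of the setting measured by the Perceived Restorativeness Scale". Differences between settings are what that scale is meant to show, so this is no defect. But with no activity held at both places, the scale cannot separate activity from place either.

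Four stronger readings are tempting, and the documents do not support them.

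- *The plan will often produce a false activity finding.* No place effect, SD or correlation is given, and only an effect that changes within a session survives the change score. With positively correlated scores, the planned test is also too conservative, not too liberal.
- *All outcomes are affected.* Pre and post measures are stated explicitly for acute mood only. Loneliness and belonging are clearly assigned to the t-test against the survey-only group.
- *Walking against citizen science is a clean activity contrast and should be primary.* Citizen science is a guided walk, so guidance is tied to it much as place is tied to planting. Session order is not described, and it is not said that both use the same preserve.
- *The activity component is uninformative.* The single-activity changes remain usable, as above.

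**Conclusion.** The concern holds, with limits. The aliasing follows from the design and needs no numerical assumption: two of three pairwise differences and the overall test mix activity with place, and no analysis of these data can undo it. How large the resulting bias is, and in which direction, is unknown. What fails is one reading, the attribution of a planting difference or a significant overall test to activity type.

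The independent-groups ANOVA contradicts the plan's own description of the design. Its true error rate depends on a correlation that the documents do not give; under positive correlations of 0.3 to 0.7 it falls from the nominal 5% to between about 1.5% and 0.02%, with a corresponding loss of sensitivity to real differences.

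**What to change.** In Statistical Considerations, question 4:

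- Replace the one-way ANOVA with a within-person model of the change scores (repeated-measures ANOVA or a mixed model with a person effect).
- Report all three pairwise differences with 95% confidence intervals, as pilot estimates.
- Label the two planting differences *activity plus place*, and state that neither they nor a significant overall test will be attributed to activity type alone.
- Describe walking against citizen science as the only comparison not aliased with center against preserve, note that guidance, session order and possibly the preserve may still differ, and do not rank it as primary.
- Report each activity's own pre-to-post change as the change seen at its place.
- Name the outcomes that enter the change-score analysis.

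In Study Procedures, question 1, state whether walking and citizen science use the same preserve.

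The cost is a few sentences, with no added participants, sessions or data. The price is a weaker claim about planting as the physical-activity level of the framework.
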